9.2.2 Prior and Concomitant Medications and Vaccinations

Prior medications are defined as those medications with a start date and end date prior to the date of first dose of trial vaccine.

Concomitant medications are medications with an end date on or after the date of first dose of trial vaccine, or ongoing.

For partial dates, refer to SAP section 9.2.4 for partial dates imputation.

9.2.3 Age at Randomization

Age at randomization will be reported in months and derived in the following way:

Age (Months) = ((Date of Randomization - Date of Birth) + 1) / 30.4375

9.2.4 Imputation of Partial Dates

Partial AE onset and medication start dates will be imputed as follows:

- If only the month and year are specified, and the month and year of the start date is not the same that of either trial vaccination, then use the 1st of the month or the date of birth, whichever is latest.
- If only the month and year are specified, then set to the date of the latest vaccine received in the same month and year. If this results in a start date after a known or partial end date, then use the 1st of the month.
- If only the year is specified, and the year of the start date is not the same as that of either trial vaccination, then use January 1st of the year of the start date or the date of birth, whichever is latest.
- If only the year is specified, then set to the date of the latest trial vaccine received in the same year.

If this results in a date that is after the known end date of the AE/medication then use the date of the earliest trial vaccination or January the 1st, whichever is the latest.

If the start date is completely unknown, then use the date of the last trial vaccination. If this results in a date that is after the known end date of the AE/medication, then use the date of the earliest trial vaccination. If this results in a start date after a known or partial end date, do not impute the start date.

Partial medical conditions start dates will be imputed as follows:

- If only the month and year are specified, then use the 1st day of the month or the date of birth, whichever is latest.
- If only the year is specified, then use January 1st of that year or the date of birth, whichever is latest.
- If the start date is completely unknown, do not impute the start date.

Partial AE resolution, medical condition stop dates and medication stop dates will be imputed as follows:

- If the event, condition, or medication is flagged as ongoing, do not impute the stop date.
- If only the month and year are specified, then use the last day of the month or the date of datacut, whichever is earliest.
- If only the year is specified, then use December 31st of that year or the date of data-cut, whichever is earliest.
- If the stop date is completely unknown, do not impute the stop date.

Dates will be presented in listings as recorded.

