### 9.1.2 Demographics, Medical History and Prior Medications

Demographic information to be obtained vill include date of birth, sex, race (and ethnicity) as described by the subject's LAR.

Medical history will also be colleged, including but not limited to any medical history that may be relevant to subject eligibility for tial participation such as prior vaccinations, concomitant medications, and previous and ongoing illnesses and/or injuries. Relevant medical history can also include any medical history that contributes to the understanding of an AE that occurs during trial participation, if it represents an exacerbation of an underlying disease/preexisting problem.

Medical history (including corresponding medication) to be obtained will include any significant conditions or diseases that have disappeared or resolved at or prior to signing of the ICF.

Adverse medical occurrences emerging during the time between signing of the informed consent and the first administration of trial vaccine will be recorded in the medical history eCRF page. If such an adverse medical occurrence is assessed as related to a screening procedure this should be recorded as an AE related to trial procedure in the eCRF.

All medications, vaccines and blood products taken or received by the subjects prior to Visit 1 (Day 1) are to be collected as prior medications.

- a) Medications: 2 months prior to Visit 1 (Day 1, day of vaccination).
- b) Vaccines: From birth up to Visit 1 (Day 1, day of vaccination).
- c) Blood products: 3 months prior to Visit 1 (Day 1, day of vaccination).

HIL-214	
Trial No. NOR-212	Page 60 of 100
Protocol DOC-00351, 3.0	1 September 2023

Concomitant medications and vaccines will be collected from Visit 1 (Day 1) to Visit 3 (28 days after the second dose).

The use of antipyretics and/or analgesic medications within 24 hours prior to vaccination must be identified and the reason for their use (prophylaxis versus treatment) must be documented. Administration of the trial vaccine should be delayed if subjects have received antipyretics within 24 hours prior to vaccine administration.

Medications taken for prophylaxis are those intended to prevent the onset of AEs post vaccination. Medications taken for treatment are intended to reduce or eliminate the presence of symptoms that are present.

These data must be written in the source documents.

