9.4 Safety

9.4.1 Adverse Events After Vaccine Doses

Unsolicited AEs will be summarized up to 28 days after each vaccine dose if:

 $1 \leq AE Start Date - Date of Vaccine Dose + 1 \leq 28$

Unsolicited adverse events starting after 28 days after the first dose of vaccine but before the second dose, or starting 28 days after second dose, will not be included in the safety summaries, but will be included in the listings.

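### The partial-date rules can date an AE before dose 1 when both doses fall in one month, dose 1 is after the 1st and the AE ended before dose 2; with the medication definitions they also leave some records neither prior nor concomitant. The impact is small.

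*SAP*

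**What the plan says.** **Month-and-year onset (SAP 9.2.4).** Where a trial dose was given in the month concerned, the first step is: "If only the month and year are specified, then set to the date of the latest vaccine received in the same month and year". The fallback is: "If this results in a start date after a known or partial end date, then use the 1st of the month". It makes no check against dose 1.

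**Year-only and unknown starts (SAP 9.2.4).** If the first imputed date is after the known end, the year-only rule says: "then use the date of the earliest trial vaccination or January the 1st, whichever is the latest". The rule for a completely unknown start also tries the earliest vaccination and then ends with: "If this results in a start date after a known or partial end date, do not impute the start date". A completely unknown stop date is left missing.

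**Which AEs are summarised (SAP 9.4.1).** For a given dose, "AE Start Date - Date of Vaccine Dose + 1" must lie between 1 and 28.

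**Where pre-dose events go (Protocol 9.1.2).** Adverse occurrences "between signing of the informed consent and the first administration of trial vaccine will be recorded in the medical history eCRF page". There are two exceptions: events related to a screening procedure are recorded as AEs (same section), and SAEs are collected from consent (Protocol 10.4.4).

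**Medication classes (SAP 9.2.2).** "Prior medications are defined as those medications with a start date and end date prior to the date of first dose of trial vaccine". By contrast, a record counts as concomitant if it ends on or after dose 1 or is ongoing.

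**The concern.** Apart from the two exceptions, a record on the AE page should begin on or after dose 1. An imputation that places it before dose 1 contradicts what is already known about the record. The error can only remove events from the 28-day tables. The month rule is also out of step with its neighbours, since the year-only and unknown-start rules both turn to the earliest trial vaccination.

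The two medication classes do not cover every record. Prior needs both a start and an end before dose 1; concomitant needs an end on or after dose 1, or ongoing status. A record whose imputed start lands on dose 1, or whose start or stop is missing, can meet neither definition. It is then absent from both tables in SAP 11.3.2.

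**Working it through.** The plan states no figure on this point, so the check applies the rules literally and counts dates.

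**AE example.** Doses on 2 May and 30 May (28 days apart); AE onset recorded as May, ended 12 May.
- First step: 30 May. This is after 12 May, so the fallback gives 1 May.
- Day count for dose 1: 1 May − 2 May + 1 = 0. For dose 2: 1 May − 30 May + 1 = −28.
- Neither lies in 1 to 28, so the AE is not summarised.

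**When it fails.** Both doses share a month only if the dose 1 day plus the interval does not exceed the length of the month. The interval is 28 to 56 days (SAP 8.0). In a 365-day year:

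| Interval | Same-month dose 1 dates | Of these, dose 1 after the 1st |
|---|---|---|
| 28 days | 7 × 3 + 4 × 2 = 29 | 7 × 2 + 4 × 1 = 18 |
| 29 days | 7 × 2 + 4 × 1 = 18 | 7 × 1 = 7 |
| 30 days | 7 × 1 = 7 | 0 |
| 31 days or more | 0 | 0 |

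The 7 and 4 are the counts of 31-day and 30-day months; February contributes none in a 365-day year. If dose 1 is on the 1st, the fallback date equals dose 1, the day count is 1 and the AE is kept.

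**Share of children in the setting, with dose 1 dates spread evenly over the year.**
- Every interval 28 days: 18/365 = 4.9%; 3000 × 18/365 ≈ 148.
- Every interval 29 days: 7/365 = 1.9%.
- Intervals even over 28 to 56 days (29 values): (18 + 7)/(29 × 365) = 25/10,585 = 0.24%; 3000 × 25/10,585 ≈ 7.

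The documents give no interval distribution. These counts come before requiring a missing start day and a known end before dose 2.

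**Only dose 2 in the month.** Doses 10 May and 20 June; AE in June, ended 12 June. The fallback gives 1 June, and 1 June − 10 May + 1 = 23, so the AE is kept. The fallback cannot precede dose 1 here.

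**Medication examples.** Doses 10 May and 14 June 2023.
- A. Start 2023, ended 1 April 2023. First step 14 June, fallback 10 May: after its own end. Not prior (start not before dose 1) and not concomitant (ended before dose 1).
- B. Start unknown, ended 1 April 2023. 14 June and 10 May both fail, so the start stays missing. It cannot meet the definition of prior and is not concomitant.
- C. Start known, stop unknown, not flagged ongoing. There is no end date to test, so it fits neither class, whether it began before or after dose 1.

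None of the three needs both doses in one month.

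**The case against.** **The AE setting is narrow.** It needs dose 1 on the 2nd or 3rd, an interval of 28 or 29 days, a missing start day and a known end before dose 2. An end recorded only as May becomes 31 May unless the data cut is earlier, so the fallback would not normally trigger. Start and end dates are documented for every AE (Protocol 10.4.1), symptoms go into the eDiary memory aid for 28 days (9.3.3), and checks for missing or inconsistent dates generate queries (12.1). All of this stands and limits the size, but it does not make the rule correct.

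**The medication tables are descriptive.** Prior medications cover only the 2 months before Visit 1 (Protocol 9.1.2), which makes year-only starts uncommon, and all records are listed (SAP 11.3.2). This also stands. Vaccines, however, are collected from birth, so incomplete dates are more plausible there.

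**Stronger readings the documents do not support.**
- A reader might infer that every same-month pair of doses loses AEs. It does not: at 28 days, 11 of the 29 same-month dates have dose 1 on the 1st, and those AEs are kept.
- A reader might infer a bias between arms. Trial arm plays no part in the rules.
- A reader might infer that antipyretic or analgesic use before a dose is hidden. Use in the preceding 24 hours must be documented with its reason (Protocol 7.3 and 9.1.2) and is a named deviation example (SAP 11.4).
- A reader might infer an effect on vaccine efficacy. AGE onset is derived separately from the eDiary (SAP 9.3.1).

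**Conclusion.** Wrong as written, with small impact. Read literally, SAP 9.2.4 with 9.4.1 removes some post-vaccination AEs from the 28-day summaries. SAP 9.2.2 with 9.2.4 leaves three kinds of medication record unclassified. No other section restores these records to the summaries, although listings show dates as recorded.

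Roughly 7 to 150 of 3000 children could be in the AE setting. The lower figure assumes intervals spread evenly over 28 to 56 days, the upper assumes every interval is 28 days, and both assume evenly spread dose 1 dates. The number of AEs lost should be far smaller, because each also needs a missing start day and a known end before dose 2. The size of the medication gap depends on the share of incomplete dates, which the documents do not give. It is probably the more frequent of the two, since it does not depend on the dose calendar.

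**What to change.** 1. **SAP 9.2.4, month rule.** If the imputed start is after the end date, use the earliest trial vaccination in that month when it is on or before the end date; otherwise use the 1st. In the example the onset becomes 2 May, the day count is 1 and the AE is kept. Events that ended before dose 1 still go to the 1st. A serious event that began before dose 1 and ended after it would be dated to dose 1, which errs towards counting it.
2. **SAP 9.2.4, year-only rule.** If the fallback is still after the end date, use 1 January or the date of birth, whichever is later.
3. **SAP 9.2.2, prior medication.** Define it as an end date before dose 1, whatever the start date. This resolves examples A and B.
4. **SAP 9.2.2, unknown stop dates.** Treat medications with an unknown stop date as concomitant by convention. The downside is slight over-counting of concomitant use.
5. **SAP 9.2.2, vaccines.** Classify them by administration date relative to dose 1, not by stop date. The documents do not say whether vaccine records carry a stop date; if they do not, step 4 applied to vaccines would turn pre-trial infant vaccines into concomitant ones.

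The cost is a few SAP sentences and minor programming.

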9.2.5 Analysis Visit Windows

The study protocol describes the timing of visits and corresponding windows. Visits are not derived for statistical analysis. Measurements from unscheduled visits are excluded from all summaries.

For immunogenicity analysis on the PPS-I analysis set, the following windows will define which results are summarized. Immunogenicity assay results will be excluded if the corresponding blood sample is collected outside of the following windows:

- Visit 2 blood collection must be between 23 days and 70 days from dose 1 vaccination date, and also before second vaccination.
- Visit 3 blood collection must be between -10 and +33 days from 28 days after dose 2 vaccination date.
- Visit 4 blood collection must be between -17 and +40 days from subject's one year of age.
- Visit 5 blood collection must be between -17 and +40 days from subject's 18 months of age.
- Visit 6 blood collection must be between -17 and +40 days from subject's two years of age.

Summaries exclude data outside of allowable visit windows as described here. Data outside of allowable windows and data from unscheduled visits will be listed.

9.2.6 Primary Observation Period

The primary objective will be evaluated using primary endpoint cases which occurred during the 6-month primary observation period starting at 28 days post-Dose 2. If the number of AGE events collected during the 6-month follow-up predicts less than 80% power (which translates into 24 predicted primary endpoint cases) for the evaluation of the primary objective, the primary observation period will be extended to 8 months, starting 28 days post-Dose 2. A decision was made to use the 6-months primary observation period.

9.2.7 Exploratory

9.3 Efficacy

9.3.1 Acute Gastroenteritis (AGE)

Clinical definition of the AGE case as per trial protocol: Individuals presenting with at least three loose or liquid stools OR at least two or more episodes of vomiting OR one or more loose or liquid stools plus one or more vomiting episodes in any 24-hour period.

An AGE event is confirmed using records of symptoms (loose or liquid stool and vomiting), reported by subjects legally authorized representative (LAR) in the eDiary: either in the symptoms log, or in the page designed to activate symptoms log once the reported number of symptoms satisfy the clinical definition of AGE event (hereafter referred as "trigger page"). Data from the "trigger page" will be used only in addition to the activated symptom log for an AGE event. The data in symptoms log are collected daily for 8-hour time intervals (00:00 to 08:00, 08:00 to 16:00 and 16:00 to 00:00). The data in the "trigger page" are collected as number of episodes of vomiting or loose/liquid stool in the last 24 hours.

An AGE event is considered confirmed at the calendar day, for which subjects LAR reported any of the following:

- at least three loose or liquid stools,
- at least two episodes of vomiting,
- at least one episode of loose or liquid stool and at least one episode of vomiting.

Only confirmed AGEs are included in the efficacy analyses, with onset date set to the calendar day when the AGE was confirmed.

Per protocol, recurrent norovirus AGE in a subject is considered a new illness according to the clinical AGE definition, if the subject has been free from clinical symptoms for at least 5 consecutive days. Therefore, the end date of an AGE event will be set to the last date with any symptom present, before 5 days of no symptoms reported by the LAR. Missing records are considered as days without symptoms in this calculation.

A day with any symptom present is defined as a calendar day when 'Yes' for symptom occurrence was reported, together with reported number of episodes >0 in any 8-hour time interval in the symptoms log, or when number of episodes >0 was reported in the "trigger page". If in the symptoms log, the LAR reported 'Yes' for the occurrence of a symptom but did not report the number of episodes, 1 will be imputed for the corresponding 8-hour time interval. These imputed data will also be used in determining event severity (Section 9.3.3).

A day of no symptoms is defined as a day when the LAR reported 'Yes' for symptom occurrence and 0 for the number of episodes or 'No' for symptom occurrence, for all three 8-hour time intervals in the symptoms log.

Derived onset and end dates for an AGE event will be used to compute event duration in days:

Derived End Date – Derived Onset Date + 1 (day).

Derivation of the onset and end date for an AGE event will be based on records within symptoms log for reported AGE event. If there are records reported in the "trigger page" within the following time interval:

[AGE start date reported in the symptoms log – 5 days; last day with any symptom present in the symptoms log +5 days],

they will also be included in the derivation. For symptoms reported on the same calendar day multiple times, the record with the greatest number of episodes for each symptom will be used.

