9.3.3 Acute Gastroenteritis (AGE) Severity

The severity assessment of AGE events will be based on the modified Vesikari scoring (see Appendix A), derived from data collected via the electronic AGE symptoms log, "trigger page" data (both collected in the eDiary), and additional information about the AGE event (treatment and medical attention), collected in the CRF.

If reported start dates for an AGE event differ between the eDiary symptoms log and the Additional Information CRF page, the CRF data with additional information will be attributed to this AGE, if the reported start date on the CRF page is within ±5 days from the start date reported in the eDiary symptoms log.

If more than one Additional Information CRF page is associated with the same AGE event, the page resulting in the worst score (i.e., emergency department visit indicated) will be selected.

The modified Vesikari score (MVS) is composed of seven items:

- 1. Diarrhea duration (days)
- 2. Maximum number loose/liquid stools in 24h (calendar day)
- 3. Vomiting duration (days)
- 4. Maximum number vomiting episodes in 24h (calendar day)
- 5. Maximum recorded body temperature
- 6. Health care provider visits
- 7. Treatment

Each item attributes a subscore ranging from 0 to 3, except for the subscore for treatment, which contributes a maximum of 2 points. The MVS is computed as sum of subscores, with a maximum MVS of 20. For the efficacy analyses and corresponding summaries of the AGE events data, missing subscore will be set to 0. A summary of the AGE events with non-imputed MVS sub-scores will also be provided.

Symptoms (vomiting, loose/liquid stools) and temperature data collected between derived onset and end date for an AGE will be used to determine duration of the symptom, maximum number of episodes and maximum temperature.

Duration of the symptom is defined as the number of calendar days with this symptom present (see Section 9.3.1) between derived onset and end dates.

Number of episodes for a symptom will be calculated for each assessment date (calendar day) as the sum of the number of episodes for 3 8-hour time intervals in the symptoms log. Maximum number of episodes will be derived over days with symptom present. For the records where a trigger page and a symptoms log are completed on the same calendar date, the record with the greatest number of episodes will be used.

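### The trigger page's 24-hour look-back can put the same vomiting on two calendar days and lift a case from MVS 8 (mild) to MVS 9 (moderate)

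*SAP*

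**What the plan says.** SAP section 9.3.1 uses two eDiary sources with different time frames. The symptoms log is kept by calendar day in three 8-hour intervals. The trigger page, which activates the log, is "collected as number of episodes of vomiting or loose/liquid stool in the last 24 hours".

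- **Symptom day (9.3.1).** A calendar day counts if the log shows episodes, "or when number of episodes >0 was reported in the" trigger page.
- **Dating of the page.** The SAP does not state this outright. Section 9.3.3 compares records "where a trigger page and a symptoms log are completed on the same calendar date", so the natural reading is that the page carries its completion date.
- **Duplicates (9.3.1).** "For symptoms reported on the same calendar day multiple times, the record with the greatest number of episodes for each symptom will be used". Section 9.3.3 has the same rule for a page and a log on one date. Neither section deals with adjacent dates.
- **Which pages enter (9.3.1).** The interval runs to the "last day with any symptom present in the symptoms log +5 days", so a page completed the next morning is included.
- **End date (9.3.1).** "the end date of an AGE event will be set to the last date with any symptom present" before five days without symptoms.
- **Duration (9.3.3).** "Duration of the symptom is defined as the number of calendar days with this symptom present", between derived onset and end.

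SAP Appendix A gives 1, 2 or 3 points for 1, 2 or at least 3 days of vomiting. Section 9.3.3 sets moderate at 9 to 10, and the primary endpoint counts moderate and severe cases. Section 6.1 declares the move from a 24-hour period to a calendar day but does not mention the trigger page.

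**The concern.** A 24-hour count taken at any time other than midnight spans two dates. At 08:00, (24 − 8)/24 = 67% of the look-back hours lie on the previous date; at 20:00, (24 − 20)/24 = 17%. These are shares of hours, not of episodes or cases. Crediting the whole count to the completion date is harmless when the page is the only record of those episodes. It is not harmless when the log already places them on the day before.

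If the log for the completion date answers no in all three intervals, that date meets both the symptom-day and the no-symptom-day definitions in section 9.3.1. The larger-count rule then settles it in favour of the page.

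What is at stake is membership of the primary endpoint. The severity cut-off is one MVS point wide, and the power statement rests on 24 primary cases.

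**Working it through.** **Check of the scale.** Six items score up to 3 and treatment up to 2: 6 × 3 + 2 = 20, which is the SAP's stated maximum.

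**Example A (illustrative).** Three vomits on Monday evening and none later. Loose stools on Monday and Tuesday, at most 4 a day. Temperature 38.6 °C, no visit, no treatment. The log records each symptom under its own date. Points are from SAP Appendix A.

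| Item | Log only | With trigger page at 08:00 Tuesday reporting 3 vomits |
|---|---|---|
| Vomiting duration | 1 day = 1 | 2 days = 2 |
| Vomiting maximum (3) | 2 | 2 |
| Diarrhea duration (2 days) | 1 | 1 |
| Stool maximum (4) | 2 | 2 |
| Temperature | 2 | 2 |
| Visits, treatment | 0 | 0 |
| **MVS** | **8, mild** | **9, moderate** |

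**Example B.** The same evening of vomiting, no diarrhea, 38.6 °C, outpatient visit, rehydration. Items in order: vomiting duration, vomiting maximum, temperature, visit, treatment.

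- Log only, or page completed on Monday evening: 1 + 2 + 2 + 2 + 1 = 8.
- Page completed on Tuesday morning: 2 + 2 + 2 + 2 + 1 = 9, and the end date moves from Monday to Tuesday.
- Log starting only on Tuesday, with Monday not entered: vomiting is 1 day and MVS stays 8, but onset is dated a day late.

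**Example C (2 to 3 days).** Three vomits on day 0 and two on day 1, 38.0 °C, outpatient visit, rehydration: 2 + 2 + 1 + 2 + 1 = 8. A page on day 2 gives 3 + 2 + 1 + 2 + 1 = 9.

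**Conditions for the shift.**

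1. The page is completed after midnight.
2. The log holds the symptom under the previous date.
3. The log shows none of that symptom on the page's date; otherwise that date is a symptom day anyway.
4. The previous date is on or after derived onset, because section 9.3.3 counts days only from onset.
5. The case would otherwise score exactly 8.
6. It otherwise meets the primary endpoint.

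For diarrhea an extra day adds a point only from 4 to 5 or from 5 to 6 days.

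**What it could do to VE (assumed values only).** Let *f* be the share of placebo primary cases that are upgraded mild cases and *m* the VE against them, with 70% VE against the rest. Then HR = (1 − *f*) × 0.30 + *f* × (1 − *m*).

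- *f* = 5%, *m* = 50%: 0.285 + 0.025 = 0.31, so VE is 69%.
- *f* = 20%, *m* = 0%: 0.24 + 0.20 = 0.44, so VE is 56%.

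Power = Φ(√D/2 × |ln HR| − 1.96). With D = 24 and HR 0.30 it is 83.9%, consistent with the SAP's statement of more than 80%. With D held at 24, the two cases give 82% and 52%.

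Removing the upgraded cases also removes events: D becomes 24 × 1.3(1 − *f*)/(1 + HR).

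- First case: 24 × 1.235/1.31 = 22.6 events, power 82%, so no gain.
- Second case: 24 × 1.04/1.44 = 17.3 events, power 71% against 52%.

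**The case against.** The strongest reply is that the double count depends on eDiary behaviour that the documents do not show. Protocol section 6.1 asks for symptoms to be recorded from the first day of onset, but it also says the log is activated once the reported episodes meet the case definition. With a Tuesday-morning activation, Monday must be entered retrospectively, and nothing says whether or how often that happens. If it is not entered, the page is the only record of Monday evening and the SAP rule rescues data. This stands, and it limits the claim to something that can happen. It does not remove the claim: the protocol asks for the first day to be recorded, and Example C needs no retrospective entry, because the log is already running when a further page is completed.

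Taking the larger of two conflicting counts is also a defensible choice on a single date, and part of the look-back does lie on the completion date. That stands too, but the rule never looks at the date before. The SAP's provision that page data are used only in addition to an activated log does not stop the page from creating a symptom day.

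A further objection concerns the remedy. If the log alone decided onset, an AGE with one vomit before midnight and one after could lose the trigger page that confirms it, or be re-dated. That would also shift the 0 to 6 day stool window in SAP section 9.3.4. This is right, and the change below leaves onset alone.

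**Conclusion.** The SAP rules as written can count the same episodes on two dates and lift a case from MVS 8 to 9. The point rests on dating the page by completion, which is inferred, and on the previous date's episodes being in the log. It is worth correcting because it affects who is a primary endpoint case and the correction is cheap.

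Three stronger readings are not supported:

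- **That this is common.** The documents give neither the share of cases at MVS 8 nor the timing of trigger-page entries.
- **That it biases the comparison between arms.** The rule is the same in both arms and does not depend on assignment. The concern is mild cases misclassified into a moderate/severe endpoint.
- **That it lowers VE or power.** A lower VE requires weaker protection against the upgraded mild cases, which the documents do not establish. The 69% to 56% range is an illustration on assumed values. In its first case, removing the upgraded cases gains no power. The argument for change is what the endpoint means.

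**What to change.** Amend SAP sections 9.3.1 and 9.3.3, for symptom duration and AGE end date only:

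- If the log for the trigger-page date reports no episodes of a symptom in all three 8-hour intervals, and the log for the previous date reports that symptom, the trigger page does not make its date a day with that symptom.
- Apply this only where the previous date is on or after derived onset. Before onset nothing is counted twice, and the end date could otherwise fall before the onset date.
- Keep the trigger page for confirming the AGE and its onset date, for the two 24-hour maximum items, and for duration on dates with no log record.
- State that the page is dated by completion, if that is so.
- List the cases whose severity category changes. At the least, add a sensitivity analysis of the primary endpoint with duration taken from the log wherever a log record exists.

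The cost is SAP wording and programming on data already collected. SAP section 6.0 provides for amendment before unblinding; after that, the analysis should be labelled post hoc, as section 5.0 requires. A few cases at MVS 9 may move to 8, slightly lowering the primary case count. Where a caregiver wrongly logged no episodes on the page's date, a true symptom day could be lost.
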